Objectives	Phase I Primary Objectives 
 • To estimate the maximum tolerated dose (MTD) and examine the dose-limiting toxicities of carfilzomib when administered in combination with rituximab, ifosfamide, carboplatin, and etoposide (C-R-ICE) in patients with relapsed/refractory DLBCL. • To assess the toxicity of dose regimen using the CTEP NCI Common Terminology Criteria for Adverse Events (CTCAE Version 4.0).
	Phase Ib Primary Objectives (Expansion Cohort) 
 • To evaluate the safety of carfilzomib (given at maximum tolerated dose [MTD] as determined in Phase I component of this study) in combination with R-ICE salvage therapy in relapsed/refractory DLBCL patients. • To achieve an overall response rate (CR and PR) of 70% after 3 cycles of C-R-ICE in patients between the ages of 18 to 75 with relapsed/refractory CD20-positive DLBCL previously treated with rituximab-based immunochemotherapy (e.g., R-CHOP, R-EPOCH, R-HyperCVAD, etc.) induction.
	Secondary Objectives 
 • To determine the feasibility of successful mobilization of autologous stem cells (i.e., minimum of 2×10^6 CD34+ cells/kg should be collected) to be used for ASCT. (if applicable) • To determine toxicities associated with C-R-ICE salvage therapy. • To determine the TTP, PFS, and OS followed by ASCT (if applicable); Disease-free survival in CR patients. • To determine the pharmacokinetics/pharmacodynamics relationship between carfilzomib's degree of proteasome inhibition and response rate along with the time course of thrombocytopenia. • To study differences in clinical outcomes between GCB and non-GCB relapsed/refractory DLBCL following therapy with carfilzomib and R-ICE. • Correlative translational research studies to include: phenotypic/genotypic analysis and functional activity (i.e., ADCC and CMC) of patient's peripheral blood mononuclear "effector" cells (PBMC), as well as ex vivo analysis of sensitivity of primary tumor cells to various combinations of carfilzomib versus bortezomib +/- rituximab; enzymatic assay for chymotrypsin-like activity to determine the degree of proteasome inhibition in primary DLBCL patient samples and patient PBMC specimens;

	explorative analysis to identify potential factors predictive of response to therapy will be performed (as part of an NIH-supported R01 grant: R01 CA136907-0Ab; PI: [name]).
Study Design	This is multi-center open-label, prospective Phase I/Ib clinical trial evaluating the safety, efficacy, and pharmacokinetics/pharmacodynamics of Carfilzomib + standard R-ICE combination therapy in adult patients with relapsed/refractory diffuse large B-cell lymphoma. The statistical design is based on a dose-finding algorithm to determine the maximal tolerated dose (MTD) of the study regimen and an assessment of the efficacy of the treatment for patients as compared to an external standard, i.e., R-ICE historical control. All enrolled patients will receive the study drug and initiation of the treatment should take place as soon as possible following study enrollment. A total of up to 30 evaluable patients will be enrolled in the Phase I/Ib component
Target Accrual and Study Duration	A maximum of 21 patients for Phase I and 9 patients for Phase Ib expansion cohort will be enrolled at Roswell Park. The number of subjects required is a function of a currently unknown dose-toxicity relationship. Accrual is expected to take up to 10 years.
Study Procedures	
Disease Evaluation: Prior to study, at time of restaging; between Cycle 2 Day 15 to Cycle 2 Day 28 following Cycle 3 but before ASCT and at the end of treatment evaluation, then every 4 months (± 2 weeks) for 1 year, then every 6 months (± 2 weeks) for 2 years, then once a year (± 2 weeks) for 2 years for a total of 5 years, then as clinically indicated. The follow up period will begin at the end of study evaluation visit for patients that became ineligible for transplant for any reason but did not meet criteria for disease progression. The follow up period for patients that go on to transplant will begin at the Day +100 bone marrow biopsy. Patients that progress at any time will be followed for survival status only on a yearly basis.
 
Adverse Events: From first dose of study drug until 30 days after receiving last dose of study drug.
 
Hematology and Chemistry: Prior to study, Day 1 of each cycle, and post treatment follow-up.
 
Performance Status: Prior to study, Day 1 of each cycle, and post treatment follow-up.
 
History and Physical Examination: Prior to study, Day 1 of each cycle, and post treatment follow-up.
 
Electrocardiogram: Prior to study

Statistical Analysis	
 Phase I: The actual sample size for the Phase I population depends on the unknown dose-toxicity profile of the treatment and the maximum sample size is 21 patients. Phase Ib (Dose expansion cohort): The sample size calculation for the Phase Ib was based on testing the hypotheses concerning the proportion of the population who experience an objective response (i.e., CR or PR) described above. This design requires a total of up to 30 patients (it will include the patients treated in the Phase I phase and 9 patients enrolled in the dose expansion cohort). This will achieve approximately 80.1% power to detect differences of 20 percentage points (50% versus 70%). 
The primary objective of the Phase I part of this study is to determine the MTD

of the proposed regimen defined as the dose of carfilzomib added to standard R-ICE chemotherapy. The basic design of the Phase I trial will utilize a standard 3+3 dose-finding scheme which is a special case of the A + B design described by Lin and Shih (2001). Rationale behind the design is nested in the assumption that both the probabilities of toxicity and efficacious response are continuous monotonic non-decreasing functions of the dose.

The objective of the Phase Ib component is examination of the efficacy and toxicity of the addition of carfilzomib to R-ICE at the MTD dose.

The primary objective of the Phase Ib component is to assess the efficacy of the study treatment arm as compared to historical control. The primary efficacy endpoint will be best overall response rate (PR+CR) within following 3 cycles of C-R-ICE therapy (as demonstrated by whole body PET-CT and dedicated CT scans following Cycle 3 of therapy).

PK/PD Analysis: A pharmacologically-driven PK/PD model will be developed to elucidate the temporal relationship between carfilzomib concentrations and the time course of proteasome inhibition, along with temporal relationships with thrombocytopenia and neutropenia. This model will allow assessment of the dose and schedule at which carfilzomib facilitates maximal proteasome inhibition and thus lead to an increase response rate, while modulating the degree of severe toxicities. In addition, the effect of concomitant administration of rituximab, ifosfamide, carboplatin, and etoposide will be incorporated into the model to assess their potential effects on efficacy and/or toxicity.

INVESTIGATOR STUDY ELIGIBILITY VERIFICATION FORM

Participant Name: (Network sites use participant initials): _____

Medical Record No.: (Network sites use participant initials) _____

Title: **Phase I Study of Carfilzomib Plus Rituximab Plus Ifosfamide Plus Carboplatin Plus Etoposide (C-R-ICE) in Patients with Relapsed/Refractory Diffuse Large B-cell Lymphoma (DLBCL)**

INCLUSION CRITERIA				
Yes	No	N/A	All answers must be "YES or "N/A" for patient enrollment.	Date
			1. Histological confirmation of relapsed/refractory CD20 positive diffuse large B-cell lymphoma. Network sites must submit slides to Roswell Park for Central Review and confirmation.	
			2. Ann Arbor Stage I – Stage IV DLBCL at the time of relapsed/refractory disease to be eligible	
			3. Measurable or assessable disease is required. Measurable tumor size (at least one node measuring 2.25 cm ² in bidimensional measurement) per CT scan, other radiological study, and/or physical exam.	
			4. Patients must have received at least 1 prior rituximab-based immunochemotherapy (e.g., R-CHOP, R-EPOCH, etc.).	
			5. ≥ 2 weeks since major surgery.	
			6. Patients must not have any significant toxicity associated with prior surgery, radiation therapy, chemotherapy, or immunotherapy, per PI discretion	
			7. Age ≥ 18 years and ≤ 75 years of age.	
			8. Life expectancy ≥ 3 months.	
			9. Karnofsky Score (KS) ≥ 50 (Appendix B).	
			10. Adequate hepatic function, with serum ALT/AST ≤ 3.5 times the upper limit of normal in the absence of a history of Gilbert's disease (or pattern consistent with Gilbert's), within 14 days prior to starting therapy.	
			11. Adequate bone marrow reserve (If patient has cytopenias due to bone marrow involvement, these requirements are not applicable): 
• Absolute neutrophil count (ANC) ≥ 1.0 × 10⁹/L within 14 days prior to starting therapy.• Hemoglobin ≥ 8 g/dL (80 g/L) within 14 days prior to starting therapy (subjects may be receiving red blood cell [RBC] transfusions in accordance with institutional guidelines).• Platelet count ≥ 50 × 10⁹/L (≥ 20 × 10⁹/L if lymphoma involvement in the pre-treatment bone marrow is found) within 14 days prior to	

INCLUSION CRITERIA

Yes	No	N/A	All answers must be "YES or "N/A" for patient enrollment.	Date
			starting therapy.	
			12. Patients must have a serum creatinine of ≤ 1.5 mg/dL; if creatinine > 1.5 mg/dL creatinine clearance must be > 60 mL/min within 7 days prior to treatment either measured or calculated using a standard Cockcroft and Gault formula. Refer to Appendix C .	
			13. Written informed consent in accordance with federal, local, and institutional guidelines.	
			14. Females of childbearing potential (FCBP) must agree to ongoing pregnancy testing and to practice contraception. Should a woman become pregnant or suspect she is pregnant while she or her partner is participating in this study, she should inform her treating physician immediately.	
			15. Male subjects must agree to practice contraception.	
			16. No known hypersensitivity to murine products.	
			17. Patients must have normal baseline cardiac function based upon echocardiogram or gated blood pool scan (MUGA) with an ejection fraction $\geq 50\%$.	
			18. Patients who test positive for HepC Ab are eligible provided all of the following criteria are met: a) bilirubin ≤ 2 x upper limit of normal; b) ALT/AST ≤ 3 x upper limit of normal; and c) clinical evaluation to rule out cirrhosis.	
			19. Specific guidelines will be follow regarding inclusion of relapsed/refractory DLBCL based on Hepatitis B serological testing as follow: 
 • HBsAg negative, HBcAb negative, HBsAb positive patients are eligible. • Patients who test positive for HBsAg are ineligible (regardless of other Hepatitis B serologies). • Patients with HBsAg negative, but HBcAb positive (regardless of HBsAb status) should have a HBV DNA testing done and protocol eligibility determined as follow: 
If HBV DNA is positive, the subject will be excluded from the study.
 
If HBV DNA is negative, the subject may be included but must undergo at least every 2 months HBV DNA PCR testing from the start of treatment throughout the duration the treatment course.
 	

Investigator Signature: _____

Date: _____

INVESTIGATOR STUDY ELIGIBILITY VERIFICATION FORM

Participant Name: (Network sites use participant initials) _____

Medical Record No.: (Network sites use participant initials) _____

Title: **Phase I/Ib Study of Carfilzomib Plus Rituximab Plus Ifosfamide Plus Carboplatin Plus Etoposide (C-R-ICE) in Patients with Relapsed/Refractory Diffuse Large B-Cell Lymphoma (DLBCL)**

EXCLUSION CRITERIA				
Yes	No	N/A	All answers must be "NO" or "N/A" for patient enrollment	Date
			1. Patients with NHL other than DLBCL; including "transformed" DLBCL.	
			2. Known to be seropositive for HIV. An HIV test is not required for entry on this protocol, but is required if the patient is perceived to be at risk.	
			3. Positive serology for HBV defined as a positive test for HBsAg. In addition, if negative for HBsAg but HBcAb positive (regardless of HBsAb status), a HepB DNA test will be performed and if positive the subject will be excluded.	
			4. Patients with symptomatic brain involvement.	
			5. Peripheral neuropathy of Grade 2 or greater severity as defined by the National Cancer Institute's (NCI) Common Terminology Criteria for Adverse Events (CTCAE) Version 4.0. Patients with Grade 2 or higher (NCI-CTC) neuropathy.	
			6. Myocardial infarct within 6 months before enrollment, New York Heart Association (NYHA) Class II or greater heart failure, uncontrolled angina, severe uncontrolled ventricular arrhythmias, clinically significant pericardial disease, or electrocardiographic evidence of acute ischemia.	
			7. Uncontrolled intercurrent illness including, but not limited to, active infection, poorly controlled hypertension, diabetes mellitus or other serious medical or psychiatric conditions that could interfere with adherence to or completion of this study.	
			8. Pregnant or breastfeeding.	
			9. Patient has received other investigational drugs within 4 weeks before enrollment.	
			10. Chemotherapy within 3 weeks of the first scheduled study treatment.	
			11. Less than 2-year disease free from another primary malignancy (other than squamous or basal cell carcinoma of the skin, "in-situ" carcinoma of the cervix or breast, superficial bladder carcinoma, or previously treated localized prostate cancer with normal PSA levels). Patients are not	

EXCLUSION CRITERIA				
Yes	No	N/A	All answers must be "NO" or "N/A" for patient enrollment	Date
			considered to have a "currently active" malignancy if they have completed anti-cancer therapy, are considered by their physician to be at less than 30% risk of relapse and at least 2 years have lapsed.	
			12. Major surgery, other than diagnostic surgery, within 2 weeks.	
			13. Known history of allergy to Captisol® (a cyclodextrin derivative used to solubilize carfilzomib).	
			14. Medical condition requiring chronic use of high dose systemic corticosteroids (i.e., doses of prednisone higher than 10 mg/day or equivalent).	
			15. Prior HDC-ASCT.	

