5.1.4 Laboratory

- Adequate hepatic function, with serum ALT/AST ≤ 3.5 times the upper limit of normal in the absence of a history of Gilbert's disease (or pattern consistent with Gilbert's), within 14 days prior to starting therapy.

- Adequate bone marrow reserve (If patient has cytopenias due to bone marrow involvement, these requirements are not applicable):
 - Absolute neutrophil count (ANC) $\geq 1.0 \times 10^9/L$ within 14 days prior to starting therapy.
 - Hemoglobin $\geq 8 \text{ g/dL}$ (80 g/L) within 14 days prior to starting therapy (subjects may be receiving red blood cell [RBC] transfusions in accordance with institutional guidelines).
 - Platelet count $\geq 50 \times 10^9/L$ ($\geq 20 \times 10^9/L$ if lymphoma involvement in the pre-treatment bone marrow is found) within 14 days prior to starting therapy
- Patients must have a serum creatinine of $\leq 1.5 \text{ mg/dL}$; if creatinine $> 1.5 \text{ mg/dL}$ creatinine clearance must be $> 60 \text{ mL/min}$ within 7 days prior to treatment either measured or calculated using a standard Cockcroft and Gault formula. Refer to **Appendix C**.

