8 GENERAL CONCOMITANT MEDICATION AND SUPPORTIVE CARE

8.1 Safety Considerations

Based upon the experience in the Phase I and Phase II clinical studies with carfilzomib, the following observations are noted:

- A “first dose effect” has been seen, which is notable for fever, chills, rigors, and/or dyspnea occurring during the evening following the first day of infusion and an increase in creatinine on Day 2, which may be the clinical sequelae of rapid tumor lysis and/or cytokine release.
- Should a “first dose” effect occur at any point during Cycle 1 or Cycle 2, treatment with high dose glucocorticoids (e.g., methylprednisolone 50 mg - 100 mg) is recommended. In addition, intravenous fluids, vasopressors, oxygen, bronchodilators, and acetaminophen should be available for immediate use and instituted, as medically indicated.
- Dexamethasone 4 mg PO/IV will be administered prior to all carfilzomib doses.
- Acyclovir or similar should be given to all subjects with a history of herpes simplex or zoster, per institutional prophylaxis guidelines, unless contraindicated.
- CrCL changes are mostly transient, reversible, and non-cumulative. All subjects should be well hydrated. Clinically significant electrolyte abnormalities should be corrected prior to dosing with carfilzomib. Renal function must be monitored closely during treatment with carfilzomib. Serum chemistry values, including creatinine, must be obtained (within 24 hours) and reviewed prior to each dose of carfilzomib. Carfilzomib must be held for subjects with a CrCL < 30 mL/min at any time during study participation.
- Subjects with active or suspected infection of any kind that required systemic treatment should not be dosed with carfilzomib until the infection has resolved and if being treated with anti-infective, the course of antibiotics has been completed.
- Thrombocytopenia has been transient and typically resolves during the week between treatments. For platelet counts \leq 50,000/mm³, carfilzomib dosing must be held before proceeding to the next cycle of C-R-ICE.
- Subjects should have anemia corrected in accordance with the Institutional guidelines.
- Carfilzomib treatment can cause nausea, vomiting, diarrhea, or constipation sometimes requiring the use of antiemetics or antidiarrheals. Fluid and electrolyte replacement should be administered to prevent dehydration.

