8.2 Guidelines for Monitoring, Prophylaxis, and Treatment of Tumor Lysis Syndrome

- Tumor Lysis Syndrome (TLS), which may be associated with multiorgan failure, has been observed in treatment Cycle 1 and Cycle 2 in some patients with MM who have been treated with carfilzomib.

The following safety measures are mandatory for all subjects:

- In addition, subjects with high tumor burden or rapidly progressing DLBCL or compromised renal function ($\text{CrCL} < 50 \text{ mL/min}$) should be considered to be at particularly high risk.

Hydration and Fluid Monitoring

- Oral hydration: All subjects must be well hydrated (i.e., volume replete). Begin oral hydration equal to approximately 30 mL/kg/day (approximately 6 – 8 cups of liquid per day), starting 48 hours prior to the planned first dose of carfilzomib. Compliance must be reviewed with the subject and documented by the site personnel prior to initiating treatment with carfilzomib; treatment is to be delayed or withheld if oral hydration is not deemed to be satisfactory.
- Intravenous Fluids: 250 - 500 mL of IV normal saline (or other appropriate IV fluid formulation) must be given before and after each carfilzomib dose during Cycle 1. If lactate dehydrogenase (LDH) or uric acid is elevated at Cycle 2, Day 1, then the recommended IV hydration should be repeated for Cycle 2. The goal of the hydration program is to maintain robust urine output, (e.g., $\geq 2 \text{ L/day}$). Subjects should be monitored periodically during this period for evidence of fluid overload.
- In subjects considered to be still at risk for TLS at completion of Cycle 1, hydration should be continued in Cycle 2, if clinically indicated. Patients in whom this program of oral and IV fluid hydration is contraindicated, e.g., due to pre-existing pulmonary, cardiac, or renal impairment, will not be eligible to participate in the clinical trial.

Laboratory Monitoring

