9 STUDY PROCEDURES

9.1 Subject Registration

All data management will be conducted at Roswell Park. Eligible patients will be entered on study centrally at the institute by the Study Coordinator. Following registration, patients should begin protocol treatment within 14 days or sooner if clinically necessary. Issues that would cause treatment delays should be discussed with the Principal Investigator at Roswell Park (or

designee). If a patient does not begin protocol therapy within 14 days following registration, the patient's registration on the study may be canceled. The Study Coordinator should be notified of cancellations as soon as possible.

Table 3. Study Calendar

Tests and Observations	Prior to Study ¹	Day 1 of Each Cycle ²	At Time of Restaging ³	Collect Stem Cell and ASCT Data (if applicable) ²⁰	Collect Post ASCT Day +100 Data ²⁰	Post Treatment Follow-Up ⁴
History and Physical Exam	X	X				X
Pulse, Blood Pressure	X	X				X
Height/Weight/Body Surface Area⁵	X	X				
Performance Status	X	X				X
Drug Toxicity Assessment		X				X ⁷
Laboratory Studies						
CBC, Differential, Platelets	X	X ⁸				X
Serum Creatinine, BUN	X	X ⁹				X
Creatinine Clearance (Appendix C)	X	X ⁹				
Serum Electrolytes	X	X ⁹				X
Ca⁺⁺, Potassium	X	X ⁹				X
ALT, AST, Alkaline Phosphatase, Bilirubin	X	X ⁹				X
Phosphorus	X	X ⁹				
LDH and Uric Acid	X	X ⁹				X
EKG	X					
MUGA or ECHO	X					
HBsAg, HBcAb¹⁰	X					
HBV DNA, Qualitative	X ¹⁰					
HCV Ab	X ¹¹					
HIV (If risk factors present)	X					
Beta-2-microglobuline (B2M)	X					
Albumin	X	X				X

Serum or Urine-βHCG (female patients)	X ¹²					
Staging						
Lumbar Puncture	X ⁷	X ¹³				X ¹³
CT Scan (Chest/Abdomen/Pelvis) and/or PET	X ⁶		X			X ²³
Bone Marrow Aspiration and Biopsy	X ²¹		X ¹⁴			X ¹⁴
Histologic Review	X ²²					X ¹⁵
Cytogenetics (e.g., Bcl-2 or c-MYC studies)	X					X ¹⁵
Sample Submission and Correlative Studies						
Lymph Node Biopsy		X ^{16,17}				
Immune Biomarker Samples		X ¹⁸				
Pharmacokinetic /Pharmacodynamic Samples²⁴			X ¹⁹			
Adverse Events	X	X	X			X ⁷

- 1 To be completed within 28 days prior to enrollment
- 2 Within 48 hours prior to Day 1 of each induction treatment cycle.

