Appendix C. Cockcroft-Gault Calculation for Creatinine Clearance

$$CrCL = \frac{[(140 - \text{Age}) * \text{Body Mass (in kg)}]}{[72 * \text{Serum Creatinine (in mg/dL)}]}$$

If the patient is female, multiply the above by 0.85. If the patient is obese (> 30% over ideal body weight), use ideal body weight in calculation of estimated CrCL.

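### The renal entry criterion can admit an older, light patient whose creatinine clearance is already below the level at which the protocol requires carfilzomib to be held

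*Combined protocol and SAP*

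**What the plan says.** Item 12 of the inclusion checklist, repeated in Section 5.1.4, reads: "Patients must have a serum creatinine of ≤ 1.5 mg/dL; if creatinine > 1.5 mg/dL creatinine clearance must be > 60 mL/min". The clearance is to be obtained "within 7 days prior to treatment either measured or calculated using a standard Cockcroft and Gault formula". A patient at or below 1.5 mg/dL meets the criterion whatever the clearance.

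The hold rule appears in both Section 7.3 and Section 8.1: "Carfilzomib must be held for subjects with a CrCL < 30 mL/min at any time during study participation".

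Three other places bear on renal function:

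- Section 8.2 says that subjects with clearance below 50 mL/min "should be considered to be at particularly high risk" for tumor lysis.
- Section 8.2 also makes patients ineligible when the hydration program is contraindicated, and gives renal impairment as one example. It sets no numeric limit, and the clause is not on the checklist.
- Table 3 schedules creatinine clearance by Appendix C before study and on treatment days, without tying the value to eligibility.

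**The concern.** An entry criterion and a mandatory hold rule should not overlap, or a patient can be registered who may not receive the study drug on the first day. Here they use different measures. Entry turns on serum creatinine, with clearance as a second test only above 1.5 mg/dL, while the hold turns on clearance alone. Cockcroft-Gault clearance falls with age and with low weight at a fixed creatinine, so the two rules can disagree.

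A patient in the overlap contributes no carfilzomib exposure while the hold lasts. If Cycle 1 is not completed, the replacement provisions in Sections 7.4.1.3 and 13 come into play. The remaining expansion cohort is small (nine patients, Section 4.2). It is open to network sites, and their instructions in Appendix E allow no exceptions to the eligibility criteria, so the written criterion decides who enters.

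**Working it through.** The plan gives no figure of its own on this point to reproduce. The check applies its formula to its limits.

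**Inputs**

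- Formula, from "Appendix C. Cockcroft-Gault Calculation for Creatinine Clearance": CrCL = (140 − age) × kg ÷ (72 × serum creatinine).
- Sex factor, same place: "If the patient is female, multiply the above by 0.85".
- Weight rule, same place: "If the patient is obese (> 30% over ideal body weight), use ideal body weight in calculation of estimated CrCL".
- Entry limits: creatinine 1.5 mg/dL, and clearance 60 mL/min above that (Inclusion 12, Section 5.1.4).
- Hold threshold: 30 mL/min (Sections 7.3 and 8.1).
- Age 18 to 75 (Section 5.1.3); no weight limit is listed.
- The example ages, weights and creatinine values are my assumptions, chosen within the permitted age range.

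**Step 1: a patient who passes entry but is below the hold threshold.** Woman, 75 y, 50 kg, creatinine 1.5:

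65 × 50 ÷ (72 × 1.5) × 0.85 = 3250 ÷ 108 × 0.85 = 25.6 mL/min.

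Creatinine is not above 1.5, so clearance is not tested for entry, yet 25.6 is below 30. The ideal-weight rule could only lower the figure.

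**Step 2: how far the overlap extends.** Setting CrCL = 30 and solving for weight gives

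kg = 30 × 72 × creatinine ÷ [(140 − age) × sex factor].

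At creatinine 1.5 and age 75: women 3240 ÷ (65 × 0.85) = 58.6 kg; men 3240 ÷ 65 = 49.8 kg. Weights below which clearance is under 30:

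| Age | Women, 1.5 mg/dL | Men, 1.5 | Women, 1.3 | Men, 1.3 | Women, 1.0 | Men, 1.0 |
|---|---|---|---|---|---|---|
| 60 | 47.6 kg | 40.5 kg | 41.3 kg | 35.1 kg | 31.8 kg | 27.0 kg |
| 70 | 54.5 kg | 46.3 kg | 47.2 kg | 40.1 kg | 36.3 kg | 30.9 kg |
| 75 | 58.6 kg | 49.8 kg | 50.8 kg | 43.2 kg | 39.1 kg | 33.2 kg |

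**Step 3: how narrow it is.** At creatinine 1.5, high age or low weight alone is usually not enough:

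- man, 75 y, 70 kg: 65 × 70 ÷ 108 = 42.1
- woman, 75 y, 70 kg: 42.1 × 0.85 = 35.8
- woman, 30 y, 45 kg: 110 × 45 ÷ 108 × 0.85 = 39.0

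All three are above 30.

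**Step 4: a patient the criterion rejects.** Man, 60 y, 85 kg, creatinine 1.6:

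80 × 85 ÷ (72 × 1.6) = 6800 ÷ 115.2 = 59.0 mL/min.

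Creatinine is above 1.5 and clearance is not above 60, so he is excluded. This uses actual weight, which Appendix C allows if his ideal weight is at least 85 ÷ 1.3 = 65.4 kg. The criterion thus admits 25.6 and rejects 59.0.

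**Step 5: whether another criterion closes the gap.** No other listed inclusion or exclusion criterion sets a minimum clearance. The hydration clause in Section 8.2 could remove some of these patients by judgment, but it has no numeric limit.

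**The case against.** The strongest reply is that the overlap is a corner case which the plan already detects. Table 3 obtains clearance in every patient before study and again on Days 1, 2, 8 and 9. Sections 7.3 and 8.1 require creatinine within 24 hours before each carfilzomib dose. A hold is not a discontinuation, and unevaluable patients are replaced in any case. All of this stands, and it limits the harm. It does not resolve the contradiction, because a patient whose low clearance is known at screening still satisfies every item on the checklist.

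It could also be said that Section 7.3 concerns retreatment, so its hold rule need not apply on Cycle 1 Day 1. Section 8.1 repeats the rule as a general safety consideration, and both places apply it throughout participation. Sections 2.1 and 7.4.2.6 describe carfilzomib use in severe renal impairment, but the hold rule stands alongside that background.

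Some stronger readings are tempting but not supported:

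- That older patients, or light patients, in general enter below 30. Step 3 shows that high age, low weight and creatinine near the limit are needed together.
- That any patient just under 60 is excluded. This is so only when creatinine is above 1.5.
- That most patients over 60 years who enter at creatinine 1.5 would fail the 60 mL/min limit. The documents give no weight distribution, and solving for the high body weights that reach 60 ignores the ideal-weight rule in Appendix C.
- That such patients enter unnoticed. Table 3 says otherwise.
- That the flag below 50 mL/min contradicts entry. It presupposes that such patients are enrolled.

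**Conclusion.** The concern holds as a specific inconsistency. Inclusion 12 and Section 5.1.4 can make a patient eligible whom Sections 7.3 and 8.1 bar from the Day 1 dose, and the same criterion can reject a patient with better clearance.

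The size is small. At the creatinine limit and the top permitted age, the overlap covers women under 58.6 kg and men under 49.8 kg, and it shrinks quickly at lower age or creatinine. How many patients fall there is unknown; I assume few. Section 4.1 has already fixed the Phase Ib dose level, so prospectively the issue concerns at most the nine expansion places and any replacements. For patients already entered it is a matter of checking the records.

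The conclusion rests on clearance calculated by Appendix C. Inclusion 12 also allows a measured value, which may differ in an individual patient.

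**What to change.** The sponsor should reconcile checklist item 12 and Section 5.1.4 with the hold rule in Sections 7.3 and 8.1, so that no patient is eligible and at the same time barred from the Day 1 dose. The clearance already collected at screening can be used for this. The same amendment should check consistency with the flag below 50 mL/min and the hydration clause in Section 8.2. Which measure and which cut-off decide entry is for the sponsor to settle.

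For patients already entered, list baseline clearance and flag any value below the hold threshold.

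The cost is a short amendment, a checklist edit and one listing, with no new test. The downside is that, depending on how the passages are reconciled, some older or low-weight patients may no longer be eligible.
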